12.5.4.2 Analysis Plan

Time to first bowel movement will be evaluated using a Cox proportional hazards model. The comparison of the two arms will be made adjusting for the variables used in the stratified randomization.

12.5.5 Quality of Life

12.5.5.1 Analysis Population

Subjects will be grouped by study intervention, with experimental subjects being compared to control subjects. Missing data will be dropped, and subjects who were non-adherent to the protocol will be excluded.

12.5.5.2 Analysis Plan

Data will be compared between the two groups using a two-tailed t-test.

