3.4 Randomization Procedures

Patients will be randomized within their surgery subtype (unilateral or bilateral) by the Stanford

Pharmacy to receive TAP catheters infusing either bupivacaine or saline. Randomization will occur using a computer software program to be implemented by the Pharmacy. The anesthetist placing the block, the surgeon performing the surgery, the nurses caring for the patient while hospitalized, and the research coordinators collecting data will be blinded to the randomization status.

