4. TREATMENT PLAN

4.1 Pre-operative clinic visit

4.1.1 All patients undergoing microsurgical breast reconstruction for breast cancer with abdominal free flap are screened for enrollment.

4.1.2 Patients meeting inclusion criteria and not meeting exclusion criteria are enrolled. (See Appendix A for further details on inclusion and exclusion criteria.)

4.1.3 Consent forms for study enrollment are signed.

4.1.4 BREAST-Q¹⁹ questionnaire filled out.

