9. STUDY CALENDAR

	Pre-Study	POD 0	POD 1	POD 2	POD 3-Discharge	1-6 months post-operatively
Investigational Treatment		X	X	X		
Informed consent	X					
Demographics	X					
Medical history	X					
Height	X					
Weight	X					
TAP catheter		X	X	X		
PCA		X	X	X		
Adverse event evaluation		X	X	X	X	
Evaluation for discharge ^a		X	X	X	X	
Pain evaluation	X	X	X	X	X	
BREAST-Q questionnaire	X					X

^aPatients will be evaluated daily for meeting discharge criteria and discharged when all criteria are met (detailed in Section 4.2.5).

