10.6 Secondary Outcome Measure: Quality of Life

10.6.1 Measurement Definition

Quality of Life is defined as the calculated score from the BREAST-Q questionnaire.¹⁹

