10.6.2 Measurement Methods

Quality of Life will be measured by having the patient fill out the BREAST-Q questionnaire pre-operatively, as well as post-operatively between 1-6 months after surgery.

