10.6.3 Measurement Time Points

Quality of Life will be measured 1-6 months after surgery.

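### BREAST-Q is compared by a t-test that uses neither the pre-operative score nor laterality, both already collected; ANCOVA on both is a near-costless improvement, and the scale analysed should be named.

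*Combined protocol and SAP*

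**What the plan says.** All references are to the combined protocol and SAP.

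- **Test.** Section 12.5.5.2 consists of one sentence: "Data will be compared between the two groups using a two-tailed t-test".
- **Population.** Section 12.5.5.1 groups patients by arm, does not mention laterality, and adds: "Missing data will be dropped, and subjects who were non-adherent to the protocol will be excluded".
- **Outcome.** Section 10.6.1: "Quality of Life is defined as the calculated score from the BREAST-Q questionnaire". Section 10.6.2 describes "having the patient fill out the BREAST-Q questionnaire pre-operatively, as well as post-operatively between 1-6 months after surgery". Section 10.6.3 gives one time point: "Quality of Life will be measured 1-6 months after surgery".
- **Baseline data.** The pre-operative BREAST-Q is collected under section 4.1 and marked in the pre-study column of the section 9 calendar.
- **Stratum.** Sections 3.4 and 12.1.1 randomise within unilateral and bilateral surgery, so laterality is known for every randomised patient.
- **Other outcomes.** Narcotic usage is grouped by laterality (12.4.1) and adjusted for the stratification variable (12.4.2). Pain is compared within laterality (12.5.1.1). Anti-emetic usage, ambulation and bowel movement are adjusted for the stratification variable (12.5.2.2, 12.5.3.2, 12.5.4.2). Section 2.3 says that the two laterality groups will be kept apart in the analysis.

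**The concern.** Two covariates that may be prognostic are in hand and the quality-of-life analysis uses neither. A pre-operative score on the same questionnaire is usually the first covariate to consider for a patient-reported outcome. Laterality is the stratification factor, and the plan treats it as important everywhere else. Leaving it out of one outcome without a reason is an internal inconsistency.

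The outcome is also under-specified. The text leans towards the post-operative score but does not exclude change from baseline, and it does not say which BREAST-Q scale or summary is the calculated score. Those choices could then be made after the data are seen. The stakes are precision, consistency and pre-specification for a secondary outcome. The primary analysis is not affected.

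**Working it through.** **Inputs from the documents.** 64 per arm, 80% power, two-tailed t-test, difference 10 mg and SD 20 mg for the primary outcome (12.6.1, 12.6.2). The documents give no BREAST-Q SD, target difference, baseline to follow-up correlation or loss rate.

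**Assumptions.** Two-sided 5% (alpha is not stated). Correlation r = 0.1, 0.3, 0.5 or 0.7. Results are in units of the BREAST-Q SD.

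**Step 1: reproduce the plan's figure.** 10/20 = 0.5 SD. The noncentral t distribution gives power 79.5% at 63 per arm and 80.1% at 64, so 64 per arm is confirmed. It also confirms the two-sided 5% level, because a one-sided test would need only 50 per arm.

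**Step 2: residual variance relative to a t-test on the post-operative score.**

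- Post-operative score, t-test: 1, with 126 degrees of freedom.
- ANCOVA on baseline and laterality, with laterality not prognostic: (1 − r²) × (1 + 2/123), with 124 degrees of freedom. The factor 1 + 2/123 = 1.016 is the cost of estimating two covariates.
- Change score, t-test: 2(1 − r), with 126 degrees of freedom. It is shown only because the text does not exclude it.

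**Step 3: difference detectable with 80% power at 64 per arm (SD units).**

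| r | Post-operative t-test | ANCOVA | Change-score t-test |
|---|---|---|---|
| 0.1 | 0.499 | 0.501 | 0.670 |
| 0.3 | 0.499 | 0.480 | 0.591 |
| 0.5 | 0.499 | 0.436 | 0.499 |
| 0.7 | 0.499 | 0.359 | 0.387 |

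ANCOVA and the post-operative t-test break even near r = 0.13. At r = 0 ANCOVA gives 0.503 SD, a loss of 0.503 − 0.499 = 0.004 SD. For a true difference of 0.5 SD (borrowed from the primary outcome for illustration), power goes from 80.1% to 79.5% at r = 0, 83.1% at r = 0.3, 89.5% at r = 0.5 and 97.4% at r = 0.7.

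**Step 4: losses.** 64 per arm is the best case. With 51 analysed per arm (assumed loss of about 20%: 64 × 0.8 = 51.2) and r = 0.5, the detectable difference is 0.560 SD for the post-operative t-test and 0.490 SD for ANCOVA. The absolute figures worsen and the comparison stands.

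**Step 5: laterality.** The figures above give it no prognostic value. In a simulation of 10,000 trials with laterality balanced between arms, strata 0.8 SD apart (assumed) and r = 0, the unadjusted t-test had type I error 3.4% and power 75.0%. ANCOVA had 4.9% and 79.5%. Ignoring a prognostic stratum therefore makes the test conservative.

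**Step 6: missing baselines.** Suppose a share m = 0.10 of patients lack a pre-operative score (assumed). Variance relative to the post-operative t-test, before the small covariate cost:

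| r | ANCOVA dropping them, (1 − r²)/(1 − m) | Overall-mean imputation, 1 − r²(1 − m) |
|---|---|---|
| 0.1 | 0.99/0.9 = 1.10 | 1 − 0.009 = 0.99 |
| 0.3 | 0.91/0.9 = 1.01 | 1 − 0.081 = 0.92 |
| 0.5 | 0.75/0.9 = 0.83 | 1 − 0.225 = 0.78 |
| 0.7 | 0.51/0.9 = 0.57 | 1 − 0.441 = 0.56 |

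A simulation of 20,000 trials, which includes the covariate cost, gave 1.11, 1.02, 0.84 and 0.57 for dropping, and 1.00, 0.93, 0.79 and 0.56 for imputation. Type I error with imputation was 4.9% to 5.3%. Without a missing-baseline rule, ANCOVA could do worse than the t-test at low r.

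**The case against.** An unadjusted t-test in a randomised trial is valid, and on a secondary outcome with no stated power or target difference the choice of ANCOVA is one of efficiency. That stands, and it limits the weight of the point. Three stronger readings are tempting and the documents do not support them.

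- **That the score is wholly undefined, or that change is planned.** Section 10.6.3 puts the measurement after surgery, and neither 10.6 nor 12.5.5 mentions change. The natural reading is a t-test on the post-operative score, so that is the fair comparator and the large change-score figures (0.670 and 0.591 SD) are not. What remains open is that 10.6.1 and 10.6.2 do not exclude change, and that no scale is named.
- **That ANCOVA is certain to gain.** Its size and even its direction depend on a correlation that the documents do not give. Below about r = 0.13, with laterality not prognostic, there is a trivial loss.
- **That the omission biases the comparison or inflates type I error.** It does neither. Where strata differ, the error moves in the conservative direction.

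It is also fair to say that a laterality term adjusts for the groups and does not separate them, so it does not meet section 2.3 to the letter. It does bring quality of life into line with the adjusted secondary analyses in 12.5.2 to 12.5.4.

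**Conclusion.** The point holds as an improvement in precision and consistency. Section 12.5.5.2 leaves two collected covariates unused, and quality of life is the only analysed outcome without any handling of laterality. Against a t-test on the post-operative score, the detectable difference changes from 0.499 SD by +0.002, −0.019, −0.063 or −0.140 SD at r = 0.1, 0.3, 0.5 or 0.7. The worst case is a loss of about 0.004 SD. These figures rest on 64 analysed per arm, two-sided 5%, the assumed correlations and a laterality effect of zero. The gain is likely but not guaranteed. It concerns a secondary outcome only and should be made, but the trial's main conclusion does not depend on it. The exclusion of non-adherent patients and the dropping of missing data in section 12.5.5.1 are a separate problem that this change does not cure.

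**What to change.** Replace section 12.5.5.2 with text such as:

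> The post-operative BREAST-Q score will be compared between arms by analysis of covariance with arm, pre-operative BREAST-Q score and laterality (unilateral or bilateral) as terms. A missing pre-operative score will be replaced by the mean of all observed pre-operative scores, both arms combined.

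This settles post-operative score against change, and no patient with a post-operative score is lost for want of a baseline. It does not by itself settle which score is meant, so section 10.6.1 should also name the BREAST-Q scale or summary to be analysed.

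**Cost.** No new data or visits, two degrees of freedom, and one protocol modification with IRB approval before implementation (section 11.1). ANCOVA is already planned for narcotic and anti-emetic usage, so no new method is needed. The change should be made before unblinding.

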12.6 Sample Size

12.6.1 Accrual estimates

Based on data from prior years of patients undergoing post-mastectomy breast reconstruction, we estimate a total of 40 patients will be eligible for study enrollment each year. This number was determined by counting the number of patients who underwent eligible surgeries in 2014 at Stanford Hospital and Clinics. If study accrual falls short of what is expected, we will apply for IRB extension and continue study enrollment until the target sample size is reached. Our target sample size is 64 patients in each the experimental and control groups for a total of 128 patients.

12.6.2 Sample size justification

The target sample size was determined by the two-tailed t-test power calculation. The estimated standard deviation of total oral morphine or equivalents is 20 mg. A difference of 10 mg between the two arms is considered clinically relevant. To detect a difference of 10mg of morphine (or oral morphine equivalents) between the experimental and control groups with a power of 80%, we calculated a target enrollment of 64 patients in each group. The null hypothesis is that the experiment and control groups will not have significantly different Post-operative Narcotic Usages in the first 48-hour period post-operatively. The alternative hypothesis is that the experiment and control groups will have significantly different Post-operative Narcotic Usages in the first 48-hour period post-operatively

APPENDIX A: Participant Eligibility Checklist

Protocol Title:	A Randomized Double-blinded, Placebo-Controlled Trial: Use of Transversus Abdominis Plane (TAP) Block in Breast Cancer Patients Undergoing Microsurgical Breast Reconstruction with Abdominal Free Flap
Protocol Number:	34315
Principal Investigator:	[name], FACS

II. Subject Information:

Subject Name/ID:
Gender:  Male  Female

III. Study Information:

SRC Approved IRB Approved Contract signed

IV. Inclusion/Exclusion Criteria

Inclusion Criteria (From IRB approved protocol)	Yes	No	Supporting Documentation*
1. Female			
2. Greater than 18 years old			
3. Undergoing microsurgical breast reconstruction with abdominal free flap			
4. Has a prior diagnosis or presumed diagnosis of breast cancer or undergoing prophylactic treatment			
5. Capable of providing informed consent			
Exclusion Criteria (From IRB approved protocol)			
1. Allergic to local anesthetics or opioids			
2. History of addiction to narcotics within last 24 months			
3. History of chronic pain on opioids within last 24 months			
4. Specific mental health issues such as schizophrenia or bipolar disorder			
5. Pregnant			

*All subject files must include supporting documentation to confirm subject eligibility. The method of confirmation can include, but is not limited to, laboratory test results,

radiology test results, subject self-report, and medical record review.

IV. Statement of Eligibility

By signing this form of this trial I verify that this subject is [**eligible** / **ineligible**] for participation in the study. This study is approved by the Stanford Cancer Institute Scientific Review Committee, the Stanford IRB, and has finalized financial and contractual agreements as required by Stanford School of Medicine's Research Management Group.

Treating Physician Signature:	Date:
Printed Name:	

Secondary Reviewer Signature:	Date:
Printed Name:	

Study Coordinator Signature:	Date:
Printed Name:
